pRQ4: To what extent do children with a peer support group report a reduction in **bullying** at the end of the intervention compared to their pre-intervention baseline level?

sRQ5: To what extent do children with a peer support group report improved **mental health** at intervention end compared to their pre-intervention baseline level?

sRQ6: To what extent do children with a peer support group report better **quality of life** at intervention end compared to their pre-intervention baseline level?

sRQ7: To what extent do children with a peer support group report increased **general self-efficacy** at intervention end compared to their pre-intervention baseline-level?

sRQ8: To what extent does the effects as measured in R1-R7 persist 6- and 9 months after intervention end compared with pre-intervention baseline level?

sRQ9: To explore the recruitment rate and factors associated with non-participation, on school, provider, and child level.

sRQ10: To describe whether the intervention was delivered according to protocol in terms of quality, quantity, adaptions and variations across schools and time.

[figure not shown]
sRQ11: To describe the intervention acceptability from children's, teachers, school nurses and residents' perspectives.

sRQ12: To investigate barriers and facilitators to intervention delivery and the mechanisms of impact.

Study design

This is a cluster randomized trial of children in 5th to 7th grade in Norwegian primary schools with randomization at school level. The cluster design is well-suited due to the significant risk of contamination between the groups with a regular RCT design. The study flow is presented in figure 1. Intervention schools will implement the SFA-model for reducing bullying, whereas the control schools will offer usual care according to national guidelines. The intervention is at two levels; (i) training of school nurses and school staff and raising awareness about the SFA-model among parents and students; for this part the outcomes will be measured at cluster-level, and (ii) implementing the SFA-model on individual participant level; for this part the outcomes will be measured on individual level in the intervention cluster only. The recruitment process, the intervention and the outcomes measured are described below.

Figure 1 Study flow for the Cluster randomized controlled trial

Methods

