The target population for the study are all school children in 5th-7th grade in primary schools in Asker, Moss and Lillestrøm municipalities in the central-eastern part of Norway. Primary schools with more than 200 students and with a school nurse appointed in at least 50% position are eligible for the study. Eligibility for having a support group established is based on the subjective experience of loneliness by the individual child and is defined as a negative emotional state caused by the discrepancy between the desired and actual social relationships, in line with Peplau et al (1).

Clusters and randomization procedure Since decisions about bullying interventions are typically made at the municipal level, we will begin the recruitment process of schools through enrolment of selected municipalities, as illustrated in figure 2. In selected municipalities consenting to participate, we will randomly invite 26 primary schools from the pool of eligible primary schools in these municipalities.

Figure 2. Illustration of the recruitment process of primary schools in xx, xxx and xxx municipalities in Norway

We will continue enrollment until the pre-identified number of schools is reached. The enrolled schools will be sorted by size and then block-randomized in a 1:1 ratio to either the intervention arm (hereafter referred to as intervention schools) or the control arm (hereafter referred to as control schools). A statistician not involved in the study will carry out the randomization procedure. After randomization, the schools will be informed about their assigned cluster and will receive more detailed information accordingly.

Sample size calculation *School level*: Based on the available literature, we anticipate that 6-10% of children in 5th -7th grade will report bullying (Krusell et al., 2019; Wendelborg, 2021). This proportion is expected to be reduced to at least 6 % in intervention schools' post-intervention. With a significance level at 5% and power at 80%, we will need 721 children in each arm. Accounting for additional variation, we would need 793 in each arm. We assume there will be three classes in each school with about 30 children in each class. Thus, we aim to include 26 schools (13 for each arm) to ensure that the study is sufficiently powered.

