Individual child level: The quality-of-life inventory KIDscreen-27 (28) has 5 domains and is scored from 0-100. For the domain "social support and peers", we anticipate a change of at least 3 points from baseline to 9 months (35). Further, when assuming a correlation of 0.7 to account for statistical dependencies (as the same child is assessed several times), and keeping significance level to 5%, we would need 55 children experiencing loneliness. To account for possible dropouts, we add additional 10% participants, i.e., 60 children.

Study procedure Essential information about the intervention, including the recruitment process and the continuation and follow-up phases will be shared with the municipality, students, parents, teachers and school nurses involved in the project. Written information about the option for support groups for children encountering challenges related to bullying at school will also be provided to parents. **Training Intervention Schools**: A group of two to three teachers or school nurses will participate in a three-day training program centered around the solution-focused approach and the support group model. This training will be led by *Adults for Children*, an organization possessing extensive expertise in implementing interventions within school settings. Following the training, the peer support group intervention will be initiated as soon as possible. **Control Schools**: In the control schools, preventive and health promotion services will be provided as usual and according to the guidelines set forth by the Norwegian Directorate of Health (29).

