Recruitment and follow-up of children experiencing bullying: The first initiative for a support group may come from the child itself or other individuals concerned about the child's well-being. Initiating a dialogue is the first step in building trust and determining if a support group could help. The child, together with the school nurse or teacher, will assess whether the support group is suitable for them. The school nurse and teachers will evaluate the child's situation carefully before recommending a support group, and if necessary, they will explore alternative follow-up options, particularly for children with complex challenges. The child experiencing bullying will not be part of the support group but will be involved in the selection of peers and will agree on what can be shared about their story with the group. The school nurse or teacher will collaborate with the child to identify 5-7 peers who could be suitable to join the group. The child is individually followed with weekly consultations with the teacher or school nurse, using an SFA-counselling approach.

Recruitment and follow-up of peers in the support group: Once peers are chosen, they are invited to the group. In the support group children are asked if they are willing to help another child. Clear boundaries will be set for peer supporters, specifically on what they may and may not share with others. They brainstorm actions they can take in the upcoming week. This transforms the group into a catalyst for improving a child's situation through small initiatives, using fellow students as a resource for change (Heitmann et al., 2022). Weekly consultations with the child and the supporting group are set up to monitor progress and brainstorm further enhancements. Peers are encouraged to concentrate on improvements and will receive acknowledgement for their progress. Sessions usually last 15-30 minutes weekly until improvement is seen. Studies indicate that the situation often improves rapidly, and in many cases, 3-5 weeks is sufficient (Heitmann et al., 2022; Kvarme, Heitman, et al., 2022; Kvarme et al., 2016; Ma et al., 2021). A comprehensive implementation manual has been developed for this intervention, and key steps are presented in table 1.

Table 1 Overview of all steps in the intervention.

The solution-focused counseling approach (SFA) is used in each step

Step 1: Meeting with the child who needs help. Create hope and identify participants for the support group.

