Step 2: Meeting with the participants that are selected to the support group. Create motivation to participate in the group and invite students to come up with suggestions to help the bullied child.
Step 3: Follow up meeting with the bullied/excluded child. In line with SFA, look for progress, create motivation and faith that he/she can contribute to make a change.
Step 4: Follow up meeting with the support group. Give positive feedback and confirm all efforts made. The progress continues until the situation improves.

Process evaluation Quantitative data from the process evaluation will provide information on fidelity, dose, and reach. Qualitative data will inform changes in implementation, experiences of the intervention and unanticipated pathways (table 2). Data will be collected at different timepoints to capture changes to the intervention over time. Process and outcome evaluators will not be completely separated which allows for data on implementation to be integrated into the analysis and interpretation of outcomes. This will also reduce the measurement burden on participants.

Outcome measures: All outcomes will be measured using validated inventories, table 2. The main outcome bullying will be evaluated with the Olweus questionnaire (Olweus., 2013). Quality of life (HRQoL) will be evaluated through the use of the Kidscreen-27 (Haraldstad et al., 2011), a validated 27-item scale.

Table 2 Overview of planned studies, outcome measures and time of measurement.

No	Population	Outcome	Outcome measure	Time of measurement	RQno ^a
Study 1	All students	Bullying Quality of life Class environment	Elevundersøkelsen-UDIR	Baseline, intervention end and after 6- and 9-months	pRQ1-3, sRQ8
Study 2 and 3	Participants with a peer support group	Bullying Quality of life Mental health General self- efficacy	Olweus ^{II} KID screen-27 ^I SDQ ^{III} GSE scale ^{IV}	Baseline, intervention end and after 6- and 9-months	pRQ4, sRQ5-8

Study 4	children, teachers, school nurses and residents	Participant perspectives on study implementation	Quantitative data Qualitative data	At implementation, intervention, intervention end and after 6 months	sRQ9-12
---------	---	--	------------------------------------	--	---------

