Furthermore, this research could offer valuable methodological insights to peer support groups and SFA in general, extending its applicability to other outcomes and amplifying its potential impact. Shifting the focus from describing the problem to promoting healthy environments in schools, through feasible and universal interventions, holds potentially noteworthy societal impact. Additionally, this research endeavour, targeting the enhancement of school health services, is both timely and essential, given the limited research directed at these services. Hence, supporting these services in adopting evidence-based approaches holds significant value. The research that is proposed in this proposal may also have an impact on the UN Sustainable Development Goal 3 (Ensure good health and promote quality of life for all, regardless of age), specifically Goal 3.d, "Strengthen the capacity for risk mitigation and management of national and global health risks."

Dissemination of results and publication policy

The results of our studies are of interest not only to target audiences directly involved in school health services, but also to the general population, policy makers, politicians and professions collaborating with school health services. Results from the study will be published in open-access, high-impact scientific peer reviewed journals, as well as in popular media, and in national and international conferences. *Adults for Children* will play a vital role in advocating for bullying children's voices during result dissemination, through popular science publications and media outreach. The Association for Public Health Nurses will actively

[figure not shown]
share project results among members via annual conferences, social media, and other outlets, also contributing to guideline revision. School nurses and teachers will collaborate with the research group, integrating implementation into the project, ensuring practical result utilization. All users will receive results pre-publication and contribute to inquiries, aiding coordinated dissemination via press, social media, and presentations.

Duration of the project

The study period is from 01.08.2024 to 01.08.028

The intervention will be implemented from September 2024 to September 2025. Figure 3 illustrates the planned timeline for the study.

Figure 3 Study progress plan with main activities and milestones

Darker color indicates that a task should be completed.

Project management

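### Does the 10% drop-out allowance fail because many 7th graders with a support group will be in 8th grade at the 9-month measurement?

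*Protocol*

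**What the plan says.** Under the individual-child part of the sample size calculation, the target quantity is a KIDSCREEN-27 domain score: "we anticipate a change of at least 3 points from baseline to 9 months". The calculation proceeds "when assuming a correlation of 0.7 to account for statistical dependencies" at a 5% significance level and arrives at 55 children. The allowance follows: "To account for possible dropouts, we add additional 10% participants, i.e., 60 children". No SD is given, and power (80%) is stated only for the school-level calculation.

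On population, Methods states: "The target population for the study are all school children in 5th-7th grade in primary schools". On timing, Duration of the project states: "The intervention will be implemented from September 2024 to September 2025". For the length of one group, the section on peers in the support group says that "in many cases, 3-5 weeks is sufficient". Table 2 gives the measurement times for children with a support group as "Baseline, intervention end and after 6- and 9-months", and sRQ8 asks whether effects "persist 6- and 9 months after intervention end compared with pre-intervention baseline level".

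Three other places bear on the point. Safety Considerations requires individual consent from parents and child for support-group participation. Table 3 plans to count drop-outs throughout the project and survey their reasons. The statistical analysis section plans mixed models for repeated measurements.

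**The concern.** Set side by side, the dates and grades suggest a predictable problem. A 7th grader whose group ends after mid-November 2024 reaches nine months after mid-August 2025 and is then in 8th grade, outside the grades that define the population. The allowance leaves a margin of 5 children (60 - 55), while one grade could supply 14-20 of the 60.

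If those children were not measured, the 9-month comparison would lose power, and the loss would fall on one grade rather than at random. These outcomes are measured in intervention schools only, as change from baseline, so no control arm would offset a selective loss. If the children were measured, their answers about peers might refer to a different peer group.

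**Working it through.** **1. Reproduce the plan's 55 and 60.** Inputs from the Protocol: difference 3, correlation 0.7, 5% level. Assumed: two-sided test, 80% power, SD 10.

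- SD of change = 10 × √(2 × (1 - 0.7)) = 7.75
- Standardised change = 3 / 7.75 = 0.387
- Paired t-test: n = 54.3, rounded up to 55, as in the plan. With SD 9 it is 45, and with SD 11 it is 66.
- 55 × 1.10 = 60.5; the plan states 60.
- Power is 84% at 60 children and 80% at 54 (60 less 10%).

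**2. Share past 7th grade at 9 months.** The Protocol gives the delivery window and the usual group length. Assumed: one third of children in 7th grade, starts spread evenly over the period shown (summer break excluded), school year changing on 18 August, groups of 4 weeks.

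One case in full: starts from 1 September 2024 to 20 June 2025, follow-up counted from the child's own group end. Four weeks plus nine months is 28 + 274 = 302 days, and 302 days before 18 August 2025 is 20 October 2024. Of 293 possible start days, 49 fall before that date and 244 on or after it. The share is 244/293 × 1/3 = 28%.

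| Group starts | 9 months from baseline | From own group end | From a common end in September 2025 |
|---|---|---|---|
| September 2024 to June 2025 | 25% | 28% | 33% |
| September 2024 to September 2025 | 21% | 24% | 29% |
| Autumn 2024 only | 10% | 19% | 33% |
| By mid-October 2024 | 0% | 0% | 33% |

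The share is driven by start pattern and time origin. The Protocol gives neither the grade mix nor the spread of starts, and it says groups begin as soon as possible after training. Figures 1 and 3 are not available here and may fix the dates.

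**3. Worst case: no child in 8th grade is measured.** At 24% and 33%:

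- Remaining of 60: 60 × 0.76 = 46 and 60 × 0.667 = 40; power 73% and 67%.
- With 10% other loss as well: 41 and 36; power 68% and 62%.
- With a mixed model that keeps these children's earlier measurements: 76% and 71%, or 71% and 67% with the other loss.

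**4. How many must be reached.** With no other drop-out, 55 remain if 9.4 of 14.4 affected children (65%) or 15 of 20 (75%) are measured. If all are measured, the plan's own 10% leaves 54, at 80% power.

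**5. Does the Protocol imply the worst case?** Grades 5-7 define who is in the target population; no passage makes them a condition for staying in follow-up. Table 2 schedules the 6- and 9-month measurements for children with a support group without a grade limit. The classroom setting in Safety Considerations follows the description of the anonymous all-student questionnaire and is not stated for the support-group instruments. The premise of step 3 is therefore not in the document.

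**The case for a change.** The strongest case for a change is one of timing. Consent wording, contact details and the enrolment target must be settled before children are enrolled, and no later analysis recovers a child nobody arranged to contact. A year-long window, with groups formed as needs arise, makes spread-out starts the natural reading, and every such reading gives at least twice the 10%. On this view, enrolment should be 55 / [0.9 × (1 - share not reached)]: about 65-67 if three quarters of these children are reached, 69-74 if half are, and 81-92 if none are.

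Part of this stands. The Protocol does not describe how a child who has left 7th grade is reached, and the 10% is not linked to grade progression. With a common end in September 2025, 7th graders from 2024/25 would already be past 7th grade at the intervention-end measurement too.

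The rest does not carry a change. The enrolment formula needs a share not reached, for which the Protocol offers no figure, and being in 8th grade is not dropping out. The power figures also depend on the assumed SD: moving it between 9 and 11 shifts the required number from 45 to 66, about as much as the re-sizing under debate. The worry about a new peer group assumes a change of school and peers that the document does not state. A 3-point difference in these children would shift the overall change by 0.7-1.0 point (0.24 × 3 to 0.333 × 3), but that difference is hypothetical.

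**Conclusion.** The arithmetic holds; the inference to a sample-size error does not. About 21-33% of support-group children would be past 7th grade at 9 months if starts are spread over the delivery window and grades are equal. The share is 0-19% if groups start in autumn 2024 and follow-up is timed per child. The fall in power to 73-67% needs a further premise, that none of them is measured. The Protocol does not say so, and Table 2 points the other way.

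The remaining gap is operational: how a child who has moved up is contacted. Individual consent, drop-out recording and mixed models are already in place, so a study team following the Protocol would fill it sensibly. With per-child timing from group end, pRQ4 and sRQ5-7 at intervention end are untouched, and the issue is confined to the later measurements under sRQ8, chiefly the one at 9 months. Enrolling more children would answer a loss that the document neither states nor implies. No change is needed.

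### Support-group sessions stop when improvement is seen and the first post-measure falls at an undefined intervention end, so on the natural reading pRQ4 and sRQ5-7 are measured at a moment partly chosen by the outcome

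*Protocol*

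**What the plan says.** **When sessions stop.** In the Protocol, Study procedure (follow-up of peers in the support group), "Sessions usually last 15-30 minutes weekly until improvement is seen". Table 1, Step 4 repeats the rule: "The progress continues until the situation improves". No maximum is given; the text says only that "in many cases, 3-5 weeks is sufficient".

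**Who judges improvement.** "Weekly consultations with the child and the supporting group are set up to monitor progress". The outcome questionnaires are not named as the basis for stopping.

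**When the outcome is measured.** pRQ4, labelled primary, asks about bullying "at the end of the intervention compared to their pre-intervention baseline level". sRQ5-7 ask about mental health, quality of life and self-efficacy "at intervention end compared to their pre-intervention baseline level". Table 2 gives the times for Studies 2 and 3 as "Baseline, intervention end and after 6- and 9-months", and gives the same times for Study 1.

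**Comparator.** None for these questions. Under Study design, "for this part the outcomes will be measured on individual level in the intervention cluster only".

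**Calendar.** The section on project duration places delivery of the programme between September 2024 and September 2025. No passage defines intervention end for an individual child.

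**The concern.** For a child with a support group, the natural reading of intervention end is the end of that child's own group. By the protocol's rule, that moment arrives when someone sees that things are better. A child's situation varies from week to week. Measuring in a week picked because it looked good gives a positive average change even if nothing has changed underneath. With no concurrent controls, nothing in the comparison removes this.

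This is separate from who enters the groups: it would arise even if entry were random. A child whose situation does not improve also has no defined end, and so no defined date for the first post-measure or for the follow-ups counted from it.

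At stake is the interpretation of one primary question (pRQ4) and three secondary ones (sRQ5-7) at their first post-measure.

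**Working it through.** **1. The two readings of intervention end.**

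- *End of the child's own sessions.* The date depends on perceived improvement: often 3-5 weeks, with no upper limit, and undefined for a child who does not improve.
- *A common date, September 2025.* The outcome does not choose the date. But a child who starts in September 2024 is measured about 12 months after baseline, and a child who starts shortly before the close is measured after a few weeks. For sessions that often last 3-5 weeks, such a mixture does not answer pRQ4 cleanly.

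**2. A scale for the size.** The protocol gives no SD for the child-level outcomes. Its child-level sample size uses 3 points on a KIDSCREEN-27 domain from baseline to 9 months, a correlation of 0.7, 5% significance and n = 55. Power is not stated there, so 55 cannot be strictly reproduced. Assuming 80% power and a two-sided test:

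- SD of change = 3 × √55 / (1.96 + 0.84) = 7.9
- SD of score = 7.9 / √(2 × (1 − 0.7)) = 10.3

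In the other direction, SD 10 gives n = 53 and SD 11 gives n = 64. So 55 is consistent with an SD of about 10, which is used below.

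**3. Simulation with no true change.** All settings are assumptions:

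- 200,000 children per scenario and score SD 10. Of the variance, 70% is stable, 20% is weekly fluctuation and 10% is measurement error.
- Weekly autocorrelation of the fluctuation is 0.5 or 0.8.
- Perceived improvement = w × (standardised change in the fluctuating state) + √(1 − w²) × noise. The weight w says how far judgement tracks the child's state.
- Sessions stop in the first week that perceived improvement exceeds 0.5 or 1. Children who have not stopped are measured at week 8, so nobody is lost.

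| Autocorrelation | w | Mean change at stop (threshold 0.5 / 1) | Rejection rate, two-sided 5% paired test, n = 55 |
|---|---|---|---|
| 0.5 | 0 | 0.05 / 0.00 | 5.0% / 5.0% |
| 0.5 | 0.3 | 0.77 / 0.87 | 12.5% / 13.7% |
| 0.5 | 0.5 | 1.25 / 1.30 | 25.8% / 24.4% |
| 0.5 | 0.8 | 1.83 / 1.85 | 48.2% / 42.4% |
| 0.8 | 0 | 0.00 / −0.01 | 5.0% / 5.0% |
| 0.8 | 0.3 | 0.24 / 0.31 | 5.9% / 6.3% |
| 0.8 | 0.5 | 0.40 / 0.49 | 7.6% / 8.3% |
| 0.8 | 0.8 | 0.69 / 0.67 | 12.4% / 10.9% |

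For w above 0, the mean stopping week is 3.2 to 5.6, close to the protocol's usual 3-5 weeks. Measured at a fixed week 5, the mean change is within 0.04 of zero in every scenario.

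**4. Wider settings.** Let the stable share be 50-70%, the weekly autocorrelation 0.3-0.8, the stopping rise 3-5 points and the maximum 12 weeks, with judgement related 0.3-0.7 to the score. The spurious change is then roughly 0.2 to 3.4 points; the limits move by a few tenths with how the noise in judgement is modelled. The upper end needs the 50% stable share, which implies a long-run correlation near 0.5 rather than the protocol's 0.7. At a fixed week 8 the change is zero.

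**5. Later time points.** sRQ8 compares 6 and 9 months with the pre-intervention baseline, not with intervention end. Even at weekly autocorrelation 0.8, the share of the excess left after 26 weeks is 0.8^26 = 0.003, or 0.3%. The bias has gone by then.

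**The case against.** The strongest objection is that intervention end is undefined, so the bias depends on a reading. Table 2 uses the same term for all students, including control schools, where no session end exists. A common programme date is therefore possible, and the implementation manual, which is not shown, may say more. This stands as a limit on certainty. It does not clear the plan, because the common-date reading has the variable-interval problem in step 1. The time point is set in the research questions and in Table 2, and no later analysis can repair measurements taken at selected moments.

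Three stronger readings are tempting, and the documents do not support them:

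- *That children who do not improve go unmeasured.* No passage says so. Table 2 assigns the measure to all participants with a support group. What is missing is a defined date for these children, so estimates restricted to improvers have no basis here.
- *That the spurious change matches or exceeds the planned effect, at about 1.7 to 5.3 points.* That range assumes staff stop on the outcome scale itself, whereas the protocol describes judgement in weekly consultations. The 3 points are also a poor yardstick: they are a 9-month change on a KIDSCREEN domain, while pRQ4 uses the Olweus questionnaire.
- *That the persistence results inherit the selected high point.* They are compared with baseline, and the excess has faded by 6 months.

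It is also fair to say that an uncontrolled before-after comparison cannot support a causal claim whatever date is used. A fixed date removes one source of bias, not all. This lowers the severity but is no reason to leave an avoidable bias in a primary question.

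**Conclusion.** The concern holds for the first post-measure in pRQ4 and sRQ5-7. On the child-level reading, the assessment date is partly chosen by the outcome and the change is biased upward. On the common-date reading, the interval varies from weeks to about a year. Either way the time point is badly fixed.

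The size rests on assumptions the protocol does not supply. With SD about 10 and judgement related 0.3-0.7 to the score, the spurious change is roughly 0.2 to 3.4 points. It is zero if judgement is unrelated to the score, and its size on the Olweus questionnaire is unknown.

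The 6- and 9-month comparisons with baseline (sRQ8), the 9-month sample-size endpoint and the randomised comparisons pRQ1-3 are essentially unaffected by this bias. Severity: should be fixed.

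**What to change.** In Table 2 (Studies 2 and 3), pRQ4 and sRQ5-7, replace intervention end with one fixed interval from each child's own baseline, beyond the usual 3-5 weeks (for example 8 weeks). Apply it to every child who starts a support group, whether or not sessions have stopped. Count the later follow-ups from that same point or from baseline. This changes only the assessment date; how sessions are delivered and when they stop are left alone.

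The cost is protocol wording and a date-driven questionnaire schedule, with no extra assessments. It has to be settled prospectively, because mistimed measurements cannot be recovered. One small downside is that a few children will still be in sessions at that measure, so the question becomes the change by the fixed date rather than at the end of sessions. The fix removes the timing bias only: regression to the mean and natural recovery remain in these uncontrolled comparisons, and the report should say so.
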